10. HUMAN SUBJECTS

Total number of subjects to be enrolled at UCSD

Our targeted sample size is 60 cLBP (30/group). We have exhibited a relatively low attrition rate on previous work, thus we request permission to enroll 74 participants with the goal of retaining 60 participants.

Age: Age will range between 18 and 65 years.

Sex: We will have equal males and females in each group. Groups will be matched by age and sex (15 males/15 females).

Ethnic background: We will include all ethnicities.

Health status: Participants must have a chronic low back pain diagnosis.

All study participants will be recruited from the ACTRI and the local community. We will employ our NIH-approved exclusion and inclusion criteria delineated in previous studies examining cLBP [27; 37; 42] as described below.

Eligibility Criteria: Patients will qualify for the study if medical evaluation demonstrates chronic low back pain that is evoked by lifting the legs. Existing medical records, per physician discretion and low back examinations will confirm diagnosis. Study physicians will confirm diagnosis (Fardon 2001, Wasan, Davar et al. 2005, Jamison, Ross et al. 2010, Wasan, Loggia et al. 2011, Fardon, Williams et al. 2014).

Inclusion criteria include those who:

- a) are between 18-65 years old;
- b) have ongoing chronic pain (pain intensity ≥ 3 on a 0-10 VAS);
- c) have radicular pain for at least 3 months;
- d) are not using other pain management procedures (i.e. CBD oil products) during the study period;
- e) are not taking opioids;
- f) if female and of a child bearing potential age, are not pregnant or nursing mothers;
- g) have not had back surgery within a year of the study start date;
- h) lack sensory/motor deficits that preclude participation in pain-inducing procedures;
- i) have no meditation experience;
- j) are straight leg raise test positive
- k) do not have any known allergies to naloxone or similar drugs

l) do not have a history of syncope and/or fear of needles/blood.

11. RECRUITMENT AND PROCEDURES PREPARATORY TO RESEARCH

Patients will be recruited through two primary streams: (1) from IRB approved flyers and recommendations by UCSD study physicians and 2) the ResearchMatch website. We will begin study recruitment after we have completed all NIH oversight requirements.

To be clear: we will post IRB approved flyers throughout the community and UCSD Pain Medicine physician offices. If a physician believes a patient is qualified for this study, they will refer the potential participant to the flyer at which point they can voluntarily call the coordinator to assess eligibility. We will not access medical records until after we have permission and the subject completes Visit 1's procedures.

Recruitment Stream 1:

The study will be advertised on ResearchMatch to gain interest for participation in the pilot to this cLBP study. This site will allow for members of the community to inquire as to their potential interests in the study's goals and requirements.

Recruitment Stream 2:

In addition, we will both advertise with flyers within these clinics that see thousands of patients each year. Hence, the sheer aggregate of potential community and clinical sources for this study would suggest more than adequate potential for our recruitment aims. The patient's treating physician will be requested to approach the participant and introduce the study. The treating physician will further discuss the research study with the potential participant and refer them to the coordinator's contact information at which point the patient has the discretion to contact the study coordinator. There will be no direct contact of the potential research participant by the study staff unless prompted by the potential participant. Their treating physicians can refer them to our study and they will call us, if they choose, on their volition.

If a potential participant is interested in the study. They will email and/or call the study coordinator to assess eligibility. This is strictly based on the patients' discretion and volition. A brief subset of preliminary eligibility criteria (such as age, gender, etc.), will be reviewed by study personnel to determine subjects' preliminary eligibility for the research study during the phone screening and Visit 1.

The phone screen script will be employed to identify preliminary study eligibility. The study team member screening potential participants, will obtain verbal consent before any participant information is collected, see item 12 below for request for waiver of documented consent for this screening. Subjects who fulfill the preliminary eligibility criteria will be offered further participation in this study.

Preliminary eligibility may be determined at the time of phone screening, but formal eligibility will only be determined after informed consent is obtained and a standard, stand-alone HIPAA authorization form is signed. The primary method of determining eligibility for the study is the straight leg raise test confirmation during Visit 1. Standard HIPAA authorization to collect research data from the patient's medical record will be obtained at the time of informed consent during Session 1. Only subjects who have consented and provided HIPAA authorization will have identifiers or linked information (e.g., subjects initials, study numbers, etc.) recorded on the Screening/Enrollment Log.

The study funder (NIH) will not have access to the subject's PHI. Only team members, as described in item 21, will have access to this information.

Strategies: Diversity and reflection of regional population. Geographically, the clinics at the ACTRI service a broad portion of the greater San Diego region. Moreover, we accept referrals from all over Southern California. As a result, our study team will recruit patients from a highly diverse patient population in terms of race, sex, and socioeconomic status. Subject populations in previous and

ongoing studies have reflected the diversity of the region and disease-specific demographics. If we are unable to obtain sufficient minority representation in our sample, under-represented racial groups will be specifically targeted for recruitment.

Contingency plans: Should the above streams of recruitment prove inadequate for us to meet our accrual timetable and keep our cohort schedule on track, we will reach out to social media and other local print and multi-media-based advertisement strategies prominent within the San Diego area. This approach has proved useful in past studies and should do so again. Participants will also be reimbursed (\$400) for successful study completion. This approach has been useful in motivating participants to complete their study responsibilities in the past. If we find that the amount offered is inadequate for maintaining active participant engagement, we will consider increasing it. This lab has had a good track record with subject accrual and retention rates.

These recruitment plans have been very successful at attaining targeted sample sizes in previous studies and have been recognized by UCSD and the NIH as appropriate models for recruitment success. The Research Plan will be amended to include these recruitment strategies (and materials if appropriate) as they are added but prior to their use.

12. INFORMED CONSENT

Waiver of Documented Consent for Aiding in Determining Preliminary Eligibility during Research Recruitment:

We are asking for a waiver of documented consent while recruiting patients to appropriately identify potential participants with chronic low back pain during the phone screening procedure.

The phone screen is considered no more than low risk to the potential participants, since we will not perform any procedure, and the probability and magnitude of harm or discomfort anticipated in this research are not greater than those ordinarily encountered in daily life. In addition, our methods of recruitment do not allow the pre-screener to directly contact or call the patient unless the patient, themselves, contacts the study team first through contact information provided on study advertisements or the patient's treating physician refers them to the study.

The information inquired about and collected from the phone screen is necessary to ascertain the potential participant's suitability for entry into the study. While reviewing responses and information during the phone screen, the screener may determine that the potential participant qualifies for the study and then proceed to ask if they would be interested in participating. The screener will indicate to potential participants that review of their medical records will be involved in determining formal study eligibility.

Consenting Procedures:

Patients will be asked to provide written consent, using an IRB-approved consent form during their first study session at the ACTRI. The consent process will take place prior to performing any study related procedures and in a private room with the door closed. The study team member will describe the study, including detailed information about risks and benefits, to potential participants. The study team member will provide potential participants with an IRB-approved consent form. Potential participants will be given ample time to read this consent form at the same visit or may take it with them to read at another time. Potential study participants will be given the opportunity to ask and receive answers to all questions they may have about the study, its risks and benefits, or the consent form itself before signing the consent form. As this research is subject to HIPAA privacy rule provisions, patients will also be requested to sign a separate HIPAA authorization for the use of protected health information. The study team member will obtain informed consent in a language understood by the prospective subject or their legally authorized representative, using certified translations of study documents that will be uploaded for IRB review and approval upon the PI's receipt of IRB approval for the English version of the document. Certified translations of study documents and qualified translators will be provided, where applicable.

Potential participants who fulfill the eligibility criteria will be offered further participation in this study. Only participants who have consented and provided HIPAA authorization will have identifiers or linked information (e.g., subjects initials, study numbers, etc.) recorded on the Screening/Enrollment Log.

All signed consents will be maintained in marked binders, secured in locked filing cabinets within private administrative offices at [name] at the ACTRI. Documentation of this process will be in written form and placed in the research record. A copy of the informed consent document will be placed in the patient's medical record, and a copy has been uploaded for IRB review and approval.

The study consent form will include:

1. Who is conducting the study
2. Purpose of the study
3. Why he/she is being asked to participate
4. What will happen during the study
5. The duration of the study
6. Potential risks
7. Potential of unforeseeable risks
8. Alternatives to study participation
9. Benefits reasonably expected
10. Care if injured
11. Costs to participate
12. Payment for participation
13. Voluntary nature of participation
14. Extent confidentiality if maintained
15. clinicaltrials.gov registry
16. Provided time to ask and answer questions
17. HIPAA discussion
13. ALTERNATIVES TO STUDY PARTICIPATION

As this is not a treatment study, the only alternative to study participation is to not participate.

14. POTENTIAL RISKS

This study may involve some risk, although the risks are considered low risk.

Straight Leg Raise Test

The straight leg raise test may produce the feeling of pain. The goal is to produce a targeted 30% increase (2-point increase) in the feeling of pain for no more than 20 minutes. Although rare (less than 2% occurrence), participants may feel discomfort and/or pain for up to 24 hours. The study team will ensure participants' comfort and/or safety during this procedure. Importantly, participants will have complete control of how much they raise their leg.

Reproductive Risks

Due to unknown risks and potential harm to the unborn fetus, sexually active women of childbearing potential must use a reliable method of birth control while participating in this study.

Pregnant women are excluded from participation in this study. Because some methods of birth control are not 100% reliable, a urine pregnancy test will be required at least 10 days from subjects' last normal menstrual period, if they are a sexually active woman of childbearing potential and not using reliable birth control.

Randomization

Participants will be instructed in the consent form with the following “You will be assigned to a study group at random (by chance). Your assignment is based on chance rather than a medical decision made by the researchers. The study group you are assigned to might not be the group you would prefer to be in. Your assigned study group might also prove to be less effective or have more side effects than the other study groups(s), or other treatments available for your condition. You will also be randomly administered either naloxone or saline (or vice versa) in experimental sessions 6 and 7 which may influence some of their responses.”

Psychological Assessments

Participants may experience eye straining while completing psychological assessments. In this rare case, we will adjust/increase the font size of our assessments on our electronic devices. Although this has not occurred in our research studies, completing psychological assessments may increase emotional distress. If this is the case, we will ask our participants to “take a break” or excuse themselves from the study. We will also refer them to counseling services if need be. There may be a perception of possible invasion of privacy or probing of information that might be considered sensitive. To address this concern, all members of the research team will be sensitive to the needs of participants by reminding them that they do not need to answer any questions that they would prefer not to answer, complete any tasks that they would prefer not to complete, or follow through with any procedure that they would rather decline. Study staff will use their clinical judgment to discontinue assessment if a participant appears upset.

Respiratory Transducer and Pulse Oximeter

During the cLBP inducing procedure, the straight leg raise test, participants will be fitted with a respiratory transducer around the chest. We have not experienced any problems with this device however, participants may feel uncomfortable with the placing of this device. We will instruct participants to inform us if that is the case, and we will make adjustments (tightening or loosening the device’s placement).

Meditation Risks

Although extremely rare, long bouts of meditation practice (greater than 3-4 hours at a time), can potentially lead to feelings of confusion, light-headedness, anxiety, sleepiness, and agitation. Further, sitting for long periods of time could cause soreness in the body. Participants will be informed at the beginning of each session that simply opening their eyes and moving could address all of these rare risks.

Naloxone

The use of high naloxone is critically needed to comprehensively antagonize endogenous opioids. This procedure is well-validated, largely safe in opioid free individuals and has reliably testing in a number of studies. However, naloxone may also worsen or exacerbate feelings of nausea, vomiting, sweating, increased heart rate, tremors, rapid breathing, and changes in body temperature, agitation, and excitement. Although extremely rare, cardiac arrest may also occur as a function naloxone infusion. Most of these side effects are mild and short-lived if they occur at all. Withdrawal symptoms can arise if patients are taking opioids. Additional care will also be provided if any of these symptoms exist. In our most recent psychophysical and pharmacologic study, 60 participants were administered intravenous naloxone and there were 0 safety events or side effects reported.

In rare cases, naloxone may cause side effects such as: nausea or vomiting, sweating, increased heart rate, tremor, rapid breathing, changes in body temperature, light-headedness, clouding of vision, fainting, agitation and/or irritability, restlessness and/or excitement. Though they are highly unlikely to occur, most of these side effects are mild and short-lived, if they occur at all. Naloxone has rarely been associated with potentially fatal cardiac arrhythmias and even flagrant cardiac arrest. Additional care will also be provided if any of these symptoms exist. Further, individuals with a history of syncope and light headedness, fear of needles and blood are excluded from this study. The ACTRI nursing

staff and/or a physician will oversee all experimental procedures where naloxone is involved to ensure complete participant safety and comfort.

Thermal Stimuli

Thermal stimuli may elicit the feeling of pain and some temporary reddening of the skin. There is the exceptionally rare potential to burning of the skin, although this has not occurred. To address this, we never strap the probe to the limb (recommended use) and have customized a probe holder that will allow the participant to escape at any time.

15. RISK MANAGEMENT PROCEDURES AND ADEQUACY OF RESOURCES

The study was carefully designed to minimize or negate any potential risk/discomfort to participants.

An Independent Monitoring Committee (IMC) will monitor the activities of this study for purposes of evaluating subject safety and study integrity. The key elements of the IMC plan include protection of participant privacy, database protection, adverse event reporting, data quality and safety reports, participant compliance, and safety review plans. For the proposed study, the IMC will review the progress of and safety after 20, 40, 60 and 74 (if needed) study participants have completed all study procedures. There will be no fee for the independent monitoring of the proposed studies. [name] will oversee all experimental procedures of the proposed research activities. In the event of an adverse safety event, protocol deviations and adverse events will be promptly (less than 24 hours) reported to the IMC and the IRB.

This study will be stopped prior to its completion if: (1) the intervention is associated with adverse effects that call into question the safety of the intervention; (2) difficulty in study recruitment or retention will significantly impact the ability to evaluate the study endpoints; (3) any new information becomes available during the trial that necessitates stopping the trial; or (4) other situations occur that might warrant stopping the trial.

We do not anticipate any events that would cause a cessation of the study. We have repeatedly demonstrated the ability to reliably recruit, retain, and execute data collection in a fashion that ensures successful completion of our experiments.

However, in the unforeseeable case that the proposed study has to be stopped, the PI will include an assessment of futility in the annual progress report to NIH. We will consult with the IMC and NCCIH to assess the impact of significant data loss due to problems associated with stopping the study.

Straight Leg-Raise Test: The straight leg-raise test is a commonly employed maneuver to examine chronic low-back pain severity and patient mobility. In the rare case that pain exacerbation is increased by greater than 4 VAS points and does not return to baseline levels after 40 minutes, we will discontinue patient study participation with reimbursement and a physician will evaluate the participant.

Pregnancy: Due to unknown risks and potential harm to the unborn fetus, sexually active women of childbearing potential must use a reliable method of birth control while participating in this study. Pregnant women and nursing mothers are excluded from participation in this study. Because some methods of birth control are not 100% reliable, a pregnancy test may be required at least 10 days from a participant's last normal menstrual period, if they are a sexually active woman of childbearing potential.

Psychological Assessments: Although there are generally very low risks to completing psychological scales, we will instruct (verbally; consent form) participants that psychological assessments may produce emotional distress. A clinical psychologist may also be available to triage any concerns.

Respiratory transducer: In order to reduce any discomfort from the respiratory transducer, we will instruct participants to “let us know” when the belt is most comfortable and/or not comfortable.

Naloxone: Naloxone will be administered intravenously. Nausea or vomiting, sweating, increased heart rate, tremor, rapid breathing, changes in body temperature; agitation and/or irritability, restlessness and/or excitement are known side effects of taking naloxone. Most of these side effects are mild and short-lived if they occur at all. Withdrawal symptoms can arise if patients are taking opioids. Thus, before any naloxone/saline infusion testing session, we will administer an opiate focused urine screening.

Thermal Stimuli: Participants will experience painful stimuli produced by heating the skin to temperatures from 35°C to 49°C. Stimuli in this temperature range have been used extensively by the PI and numerous laboratories around the world and do not produce tissue damage or burns. In order to facilitate escape from the stimulator, the stimulator will be attached to a custom-designed thermal stimulation probe holder. Participants will place their calf on top of the probe holder and will not be strapped in or otherwise restrained. Therefore, participants will be able to simply lift their legs at any time. Furthermore, stimulus temperature will be monitored continuously with an external digital chart recorder that is independent of the microprocessor in the stimulator. Specifically, the unprocessed output of the temperature sensor in the head of the stimulus probe will be both monitored and recorded. In the event of a significant deviation from the target temperature, the TSA-II is designed to shut off automatically. If the device does not shut itself off, the operator will terminate stimulation. Furthermore, all volunteers will be conscious, lift their legs (respectively) from the probe, and will be free to terminate the stimulus. In the remote event that a burn does occur, the affected area will be gently rinsed with cold water and covered with a protective bandage. The participant will then be referred to the burn clinic for treatment.

All study participants will provide informed consent. They will be reminded that their behavioral data is confidential and that they can refuse to participate and/or withdraw from study participation without explanation and financial reimbursement and this would not affect their respective relationship with their physicians.

The proposed study will be conducted in a way that assures protection of the rights and welfare of subjects. The ACTRI has an established history of successfully and safely completing clinical studies. The proposed NIH sponsored 1-year project has plenty of time to ensure completion. The ACTRI is a world-renown facility known for employing the highest standards of clinical research excellence. We will conduct Sessions 1, 6, and 7 at this facility. All intervention sessions will be conducted at the UCSD Center for Mindfulness, an established leader in conducting behavioral interventions. All research staff will be trained to reliably conduct all activities. This project will include the study team members noted in item 21 below. Due to the low risk of the study, we do not anticipate emergency medical care services.

As in the naloxone studies previously conducted by this research lab, we are solely using an opiate-focused urine drug screening as a precautionary measure to avoid any conflict, withdrawal, or side effects that naloxone would elicit if a subject was presently using opiates/opioids. It is an eligibility requirement that participants are not taking opioids. We will inquire about this thoroughly with each participant through self-report and medical history confirmation, to ensure maximum safety.

Adverse Event: An AE is any problematic medical occurrence in a subject during participation in the study.

The Office for Human Research Protections (OHRP) considers unanticipated problems involving risks to

subjects or others to include, in general, any incident, experience, or outcome that meets all of the following criteria:

- Unexpected in terms of nature, severity, or frequency given (a) the research procedures that are described in the protocol-related documents, such as the IRB-approved research protocol and informed consent document; and (b) the characteristics of the subject population being studied.
- Related or possibly related to participation in the research (“possibly related” means there is a reasonable possibility that the incident, experience, or outcome may have been caused by the procedures involved in the research); and
- Suggests that the research places subjects or others at a greater risk of harm (including physical, psychological, economic, or social harm) than was previously known or recognized.
- Any unanticipated problems, serious/unexpected adverse events, deviations or protocol changes will be promptly reported to the IRB and IMC.

Serious Adverse Event (SAE)

A serious adverse event (SAE) is one that meets one or more of the following criteria:

- Results in death
- Is life-threatening (places the subject at immediate risk of death from the event as it occurred)
- Results in inpatient hospitalization or prolongation of existing hospitalization
- Results in a persistent or significant disability or incapacity
- Results in a congenital anomaly or birth defect

An important medical event that may not result in death, be life threatening, or require hospitalization may be considered an SAE when, based upon appropriate medical judgment, the event may jeopardize the subject and may require medical or surgical intervention to prevent one of the outcomes listed in this definition.

Time Period and Frequency for Event Assessment and Follow-Up: Unanticipated problems will be recorded in the data collection system throughout the study. The PI will record all reportable events with start dates occurring any time after informed consent is obtained until 7 (for non-serious AEs) or 30 days (for SAEs) after the last day of study participation. At each study visit, the PI will inquire about the occurrence of AE/SAEs since the last visit. Events will be followed for outcome information until resolution or stabilization.

To assess relationship of an event to study intervention, the following guidelines are used:

1. Related (Possible, Probable, Definite)
 1. The event is known to occur with the study intervention.
 2. There is a temporal relationship between the intervention and event onset.
 3. The event abates when the intervention is discontinued.
 4. The event reappears upon a re-challenge with the intervention.
2. Not Related (Unlikely, Not Related)

There is no temporal relationship between the intervention and event onset. An alternate etiology has been established.

Expectedness of SAEs: The study PI and the IMC will be responsible for determining whether an SAE is expected or unexpected. An adverse event will be considered unexpected if the nature, severity, or frequency of the event is not consistent with the risk information previously described for the intervention.

Severity of Event: The following scale will be used to grade adverse events:

Mild: no intervention required; no impact on activities of daily living (ADL)

Moderate: minimal, local, or non-invasive intervention indicated; moderate impact on ADL

Severe: significant symptoms requiring invasive intervention; subject seeks medical attention, needs major assistance with ADL

Reporting Procedures: SAEs that are unanticipated, serious, and possibly related to the study intervention will be promptly reported by the principal investigator to the IRB and IMC. Anticipated or unrelated SAEs will be handled in a less urgent manner but will be reported to the IMC, UCSD IRB, NCCIH, and other oversight organizations in accordance with their requirements. In the annual AE summary, the IMC Report will state that they have reviewed all AE reports.

Confidentiality During Adverse Event (AE) Reporting: All adverse event (AE) reports and annual summaries will not include subject or group-identifiable material. Each report will only include subjects' SIDs. Any unanticipated problems, serious and unexpected adverse events, deviation/protocol changes will be promptly reported by the PI to the IRB and IMC. AE reports and annual summaries will not include patient or group-identifiable material. Each report will only include subjects' SIDs.

Data and Safety Monitoring: The PI and the IMC will be responsible for the overall monitoring of the data and safety of study participants. The PI will be assisted by other members of the study staff.

Reporting of Unanticipated Problems, Adverse Events or Deviations: Any unanticipated problems, serious and unexpected adverse events, deviations or protocol changes will be promptly reported by the PI or designated member of the research team to the IRB and NIH or appropriate government agency if appropriate.

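### Scheduled IMC safety reviews are counted on completers, so they come later as withdrawal rises, and the plan gives the IMC no defined route to adverse event rates by drug or training group

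*Protocol*

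**What the plan says.** Protocol section 15 sets the schedule: "the IMC will review the progress of and safety after 20, 40, 60 and 74 (if needed) study participants have completed all study procedures". The same section has a leg-raise rule under which, after a defined pain exacerbation, "we will discontinue patient study participation with reimbursement and a physician will evaluate the participant". Its first criterion for stopping the trial is that "the intervention is associated with adverse effects that call into question the safety of the intervention".

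On content, section 15 says: "All adverse event (AE) reports and annual summaries will not include subject or group-identifiable material". It adds: "Each report will only include subjects' SIDs". Its paragraph on expectedness makes the principal investigator and the IMC jointly responsible for deciding whether a serious event is expected, and frequency is one of the features to be compared with the known risk.

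Section 9 (Drug Administration) limits knowledge of drug assignment to the study physicians, the research pharmacist and the study coordinator. Section 9 (Sample Size Determination & Power) assumes 20% dropout and randomises 74, 37 per group. Section 10 says: "we request permission to enroll 74 participants with the goal of retaining 60 participants".

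Three provisions work the other way. Section 15 sends adverse events to the IMC and IRB in under 24 hours. It also has the IMC confirm, in the annual summary, that it has reviewed all adverse event reports. Section 16 opens all study records to the IMC whenever it wishes.

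**The concern.** A safety review should come no later when more participants are being lost. A completer count does the opposite. Someone who leaves after the first infusion has been exposed to study procedures and perhaps to naloxone, but does not bring the review closer. If harm drives withdrawal, the cumulative look is postponed in the situation where it matters most.

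The second issue is what the IMC can conclude when it meets. Deciding that harm is associated with an intervention, or that an event is more frequent than expected, takes event counts and denominators by drug, and possibly by training group. The plan describes no report to the IMC that contains them.

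**Working it through.** **Inputs.** Triggers of 20, 40, 60 and 74 completers (section 15); 20% loss and 74 randomised (section 9); cap of 74 and goal of 60 (section 10). Loss rates of 5%, 10% and 30% are assumptions, used only to show a range.

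**The plan's own figure.** Number to randomise = completers / (1 − loss) = 60 / 0.80 = 75. By group, 30 / 0.80 = 37.5, rounded up to 38, or 76 in all. The stated 74 is within two of either; it corresponds to a loss of 1 − 60/74 = 18.9%.

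**When the reviews fall.** The same formula gives the number randomised when each count is reached:

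| Loss | 20 completers | 40 completers | 60 completers |
|---|---|---|---|
| 10% | 22 | 44 | 67 |
| 20% | 25 | 50 | 75 |
| 30% | 29 | 57 | 86 |

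At 20%, with losses treated as independent, the 5th to 95th percentiles are 21–29, 45–56 and 68–83. The reviews therefore fall about 5, 10 and 15 participants later than a count of participants randomised. People still in progress at the trigger come on top.

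**Against the cap.** Expected completers = 74 × 0.80 = 59.2. The binomial chance of at least 60 completers out of 74 is about 0.48 at 20% loss and 0.99 at 10%. The fourth review needs all 74 to finish: 0.80^74 is about 7 in 100 million, and even at 5% loss 0.95^74 is about 0.02.

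**How many of these were infused.** The 20% covers all reasons, and the protocol does not say when losses occur. If all came before Session 6, 20 completers would mean 20 people infused; if all came after the first infusion, 20 / 0.80 = 25. Leaving aside those in progress, the number infused lies between 20 and 25 at the first review, 40 and 50 at the second, and 60 and 74 (the cap) at the third.

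**What the IMC must judge, and what it is given.**

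- The first stopping criterion calls for a judgement that harm is associated with the intervention. The reports described carry participant numbers and no group.
- The expectedness test uses frequency. A frequency on naloxone needs events and infusions counted by drug, and the IMC is not named among those who know the drug.
- Section 15 names data quality and safety reports as part of the IMC plan but does not give their content.

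**The case against.** The strongest reply is that scheduled counts are not the IMC's only source. Events arrive within 24 hours, participants are asked about events at every visit, each event is rated for relatedness, the annual check does not depend on completers, and any record can be requested. All of this stands. Events in non-completers are not withheld, and each notice gives the IMC a reason to ask for more. What these routes do not provide is a planned cumulative comparison with denominators. The annual check may occur only once or so, since section 4 foresees 12 months of accrual and 16 months of data collection. Section 15 also handles anticipated or unrelated serious events less urgently, which should be reconciled with its 24-hour rule.

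It can also be said that group elsewhere in the protocol means the training arm, with drug a separate factor. That is correct. The confidentiality wording does not by itself require naloxone and saline to be pooled, and leaving the IMC off the list of those aware of assignment is silence, not a ban. The gap is an undefined route.

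Finally, event rates may be low. Section 9 reports four minor side effects in over 180 earlier participants. At 4/180, 20 naloxone infusions would give 20 × 4/180 = 0.4 events; if only half of those participants received naloxone (an assumption), 0.9. An early by-drug table would usually be nearly empty. That limits the expected yield, but the table is meant for the case in which experience departs from expectation.

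**Conclusion.** The point holds as a modest, cheaply corrected weakness in the scheduled cumulative review. At the protocol's 20% loss the first three reviews come about 5, 10 and 15 randomised participants late, the third is about as likely as not to be reached under the cap, and the fourth is practically unreachable. These figures rest on the stated loss rate and on independent losses. The share that concerns infused participants depends on when losses occur, which the protocol does not say. The absence of a defined route to rates by drug or training group rests on the text alone.

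Stronger readings are not supported:

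- A reader might infer that only the reviews at 20 and 40 can affect anyone. At 10% loss about 67 are randomised when 60 complete, so some 7 of the 74 could still benefit, and the review at 74 is marked as conditional.
- A reader might infer that stopping for safety depends on the scheduled reviews. Section 15 ties none of its stopping criteria to them, and it also allows stopping for new information or other situations.
- A reader might infer that harm goes unseen, or that the IMC is barred from allocation data. The 24-hour notices and open access to records contradict both.
- A reader might expect much longer delays or a striking contrast between drugs. The documents give no withdrawal rate above 20% and no event rate that would support either.

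**What to change.** In section 15, trigger the IMC reviews at 20, 40 and 60 participants who have started their first infusion. State that each review covers everyone infused at least once, whether or not they completed. Drop the 74-completer trigger. The third review would then fall while up to 74 − 60 = 14 participants under the cap had not yet been infused.

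In the section 15 paragraph on confidentiality of adverse event reporting, keep investigator-facing reports free of group. Add a closed table, for the IMC only, of adverse events and withdrawals by drug and session, with denominators. The research pharmacist holds the drug codes (section 9), and drug symptoms are already assessed after each infusion session, so no new data are needed. The pharmacist is not said to hold training assignment; that can be added from the randomisation log kept by the coordinator (section 9, Patient Randomization).

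The cost is a wording change and one table per review. The downside is that IMC members would see allocation and must keep it confidential; the investigators' blinding is unchanged.
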